## **Methods: Data collection, management, and analysis**

### **18a) Data collection methods**

Recruitment data (CRF 1 - Appendix 7): Recruiting clinics will collect anonymous data on the characteristics of patients who were approached for the trial but declined to participate using a study recruitment log sheet. This will include age, sex and factors that make them eligible for DOT.

Baseline Data (CRF 2 – Appendix 8): Study or clinic nurses will collect baseline data at the time of initial recruitment. This mainly consists of data already routinely collected by clinics, covering patient demographics, disease categorisation and factors that make them eligible for DOT. It will also include the validated EQ-5D quality of life scale and information on employment status and approximate weekly salary

VOT/DOT diary (CRF 3 – Appendix 9):

This will be recorded by the DOT observer at the time of the scheduled session and by the VOT observer at the time of reading scheduled video clips. DOT/VOT observers will be trained to complete (CRF 3 – see section 18a) consistently. CRF3 will be faxed/emailed on a weekly basis to the study centre with the study centre following up with DOT observers when weekly forms are not returned. CRF3 will be completed directly at the study centre on the VOT reading system.

The VOT reading system includes: fields to identify when doses are scheduled; when clips are submitted and read and the following categorisation of clips:

Patient took meds?

- Y (Yes, all meds)
- P (Probably)
- S (Yes, some meds)
- N (No meds taken)
- U (Unable to tell)
- DNA / Did not send clip

This data will be used for the primary outcome and secondary adherence outcome measures.

The system also collects additional data on video and audio quality. The system collects data on geo-location at the time of recording. This will be collected if the participant provides separate consent for this.

DOT: A DOT diary will be completed by DOT observers showing when doses are scheduled to be observed, whether or not the participant attended, when they attended and whether they took the medicines categorised as above.

Patient 2 and 6 month follow up (CRF 4a & 4b – Appendix 10): The study team will contact the participant by telephone to complete a 5 minute questionnaire covering

- Quality of Life (EQ5D)
- Participant satisfaction (Likert scale)
- Participant resource use for DOT/VOT (Participant time, missed work)
- Employment
- Hospitalisation

VOT/DOT observer 2 and 6 month follow up (CRF 5a & 5b – Appendix 11): This will be completed by the VOT/DOT observer and contain the following information.

- Time spent on average observing doses over 2 or 4 month period (including travel time where relevant) – staff band and employer.
- Time spent re-engaging patients with DOT/VOT.
- Travel costs to meet with patients for re-engagement

sputum sample: At the outpatient appointment closest to 2 months after randomisation the clinic nurse will request a sputum sample and submit this to the local microbiology laboratory for smear and culture.

End of VOT/DOT participant engagement (CRF 6 – Appendix 12):

Semi-structured interviews will be performed with a purposively sampled subset of DOT and VOT participants to understand issues related to provision of DOT/VOT.

12 month follow up (CRF 7 – Appendix 13): The study data manager will work with PHE to link the participant register with national surveillance data to ascertain the following routinely recorded variables.

- Treatment outcome at 12 months (Completed, loss to follow up, transferred out, died)
- Acquisition of new resistance
- Membership of a transmission cluster (based on data from national strain typing service recorded in Enhanced surveillance)

Processes to promote data quality include:

- Training of study and clinic nurses
- Training of DOT and VOT providers
- Weekly submission of DOT diaries + Weekly VOT summary report
- Chase up of DOT provider if weekly forms not submitted
- Quality control visits to clinics every 3 months
- Double data entry for all paper-based CRFs

**18b Plans to promote participant retention and complete follow-up, including list of any outcome data to be collected for participants who discontinue or deviate from intervention protocols**

The study is predicated on maintaining regular contact with participants to monitor adherence.

Participants who are lost to follow up but have not withdrawn from the study, scheduled observations after loss to follow up will be recorded as not having been completed. It will also remain possible to obtain their final outcome data from national tuberculosis surveillance. For participants in the DOT arm who clinics decide to step-down care from DOT to self-administered therapy data will be collected on outpatient clinic attendance and collection of medications.

**19) Data management**

All data entered onto paper questionnaires will be double entered into the master data base with automatic range checks where appropriate. VOT data from the VOT reading system will be held on a secure NHS compliant server which hosts the VOT system which will be

backed up nightly. Weekly data integrity reports will be run on the system using automated routine. Monthly data exports will be made and data merged into the master data file. The master data file will be stored on a UCL password protected network with access restricted to study personnel. This will be backed up automatically on a daily basis. The master data file will use the unique study number allocated at the time of randomisation but will not include personal identifier information. This identifiable information will be held in a separate password protected file on the same network drive in the form of a look up table.

## **Statistical methods**

### **20a) Statistical methods for analysing primary and secondary outcomes.**

Characteristics of those randomised and those not randomised due to refusal or exclusion criteria will be compared. Baseline characteristics of those randomised to intervention and control arms will be compared to check for balanced randomisation. An intention to treat analyses will be used. Categorical outcomes will be compared across groups using the chi-square test or Fisher's exact test as appropriate. Continuous variables will be compared across groups using the Wilcoxon rank-sum test.

For some DOT schedules weekend doses are planned to be self-observed due to difficulty in providing DOT at the weekend. For the primary outcome these doses will not be considered in the denominator of scheduled doses, however, as this is a valuable advantage of VOT, secondary analyses will include these weekend doses as part of the treatment schedule). When participants are in hospital their dose will be considered to have been observed. When participants are in prison or custody the dose will be considered to have been observed if it can be verified with offender health that they were aware of the treatment regime. When patients are out of the country VOT participants will be encouraged to continue to take VOT clips which can either be submitted via a wifi connection or will automatically submit on return to the UK. Doses due during time abroad will not be considered as part of the primary outcome for either arm, but will be included in the secondary analyses to explore the potential value.

Patients who cross-over trial arms (see section 11b) prior to the end of 2 month follow up will be considered a failure for the primary outcome.

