**8) Description of trial design.**

The TB Reach VOT trial is designed as a randomised, controlled, analyst blinded multicenter superiority trial with two parallel groups (VOT and DOT) with a 1:1 allocation and a primary endpoint of 80% of doses being observed over a 2 month period.

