## 12) Outcomes

### *Primary Outcome Measure:*

Proportion of participants having more than 80% of scheduled VOT/DOT sessions successfully completed in the 2 months following randomisation (binary aggregation) in participants with a minimum of 6 weeks follow up data.

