#### **14) Sample size:**

A widely used programmatic measure of acceptable adherence is that patients are known to have taken at least 80% of their scheduled doses. This is particularly important early in treatment. We therefore define an adherent patient as one who is observed to take over 80% of their treatment and will compare the proportion of patients who are adherent in each arm over the first 2 months from randomisation as the primary outcome.

We have examined the power implications of a range of realistic differences in the primary outcome with 90% power at the 5% significance level (2 sided) with equal numbers in intervention and control arms of a superiority trial (table 1).

We have reviewed adherence data from Cohort review of TB patients and the VOT pilot and this suggests the 3rd or 4th scenarios are realistic.

Table 1 – Sample size needed at differing estimates of adherence and effect size.

	50% vs 70%	40% vs 60%	65% vs 80%	60% vs 75%
Intervention	121	126	181	200
Control	121	126	181	200
Total	242	252	362	400

We will aim to recruit 400 participants into the trial over a two year period.

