## **Methods: Assignment of interventions (for controlled trials)**

Allocation:

16a) Sequence generation

We will use computer generated randomisation by minimisation to ensure balance across study sites and stage of treatment at which recruitment took place 1) at start of treatment; 2) after start but within first 2 months of treatment; 3) After first 2 months of treatment.

This will ensure that treatments are balanced within the two strata.

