### **20b) Methods for any additional analyses (eg, subgroup and adjusted analyses)**

Where there is evidence of unbalanced randomisation, secondary analysis of unbalanced variables will be adjusted for in analyses, if they are associated with outcome, using multivariable regression models as appropriate. An assessment of potential effect modifiers will be performed using interaction terms in the statistical models. If there is evidence of interaction effects will be reported in subgroup analyses.

**20c) Definition of analysis relating to protocol non-adherence (eg, as randomised analysis), and any statistical methods to handle missing data (eg, multiple imputation)**

Approaches such as the sensitivity analysis described in Carpenter et al will be explored to assess whether the data are not “missing at random” before using multiple imputation to infer missing data points.

Patients who cross-over trial arms (see section 11b) prior to the end of 2 month follow up will be considered a failure for the primary outcome. Data post cross over will be considered in a separate analysis comparing adherence during periods of VOT with adherence during periods of DOT.

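### Allocation is minimised on site and treatment stage, but the primary chi-square test ignores both factors and is conservative if either predicts adherence

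*Protocol*

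**What the plan says.** - **Allocation (section 16a).** The protocol uses "computer generated randomisation by minimisation to ensure balance across study sites and stage of treatment at which recruitment took place". Stage has three levels: at the start of treatment, after the start but within two months, and later than two months. Section 8 describes "two parallel groups (VOT and DOT) with a 1:1 allocation".
- **Primary outcome (section 12).** It is binary: whether more than 80% of scheduled sessions were "successfully completed in the 2 months following randomisation (binary aggregation").
- **Primary test (section 20a).** "Categorical outcomes will be compared across groups using the chi-square test", or by Fisher's exact test where that suits better. This covers the primary outcome. Neither stratification nor covariates are mentioned.
- **Adjustment (section 20b).** Where randomisation looks unbalanced, "secondary analysis of unbalanced variables will be adjusted for in analyses, if they are associated with outcome".
- **Adjustment (section 13).** Balancing on stage is expected to make prior time on DOT similar between arms. Any imbalance is to be controlled for, here without the condition of association with outcome.
- **Sample size (section 14).** Scenarios are calculated "with 90% power at the 5% significance level (2 sided"), and "We will aim to recruit 400 participants into the trial over a two year period", which matches the 60% against 75% scenario.

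**The concern.** Minimisation removes most of the between-arm variation that site and stage could cause. The chi-square standard error still counts that variation as if the arms could differ freely on both factors. When either factor predicts adherence, the test statistic varies less than its reference distribution assumes, so p-values are too large on average. An interval built on the same standard error would be too wide.

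The adjustment rules do not repair this. Both are triggered by observed imbalance, and these are the two variables that the design keeps balanced. The reason to adjust for a minimisation factor is that it was used in allocation and predicts outcome, not that it turned out unbalanced.

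The factors could plausibly matter. Section 11a leaves DOT to each clinic's usual practice, with differing settings and optional incentives, and section 14 treats adherence early in treatment as especially important. At stake is efficiency and correct calibration of the main result.

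**Working it through.** **1. The plan's own figure.** Inputs from section 14: 60% against 75%, two-sided 5%, 90% power. The unpooled two-proportion formula is

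n per arm = (z₀.₉₇₅ + z₀.₉₀)² × [p₁(1−p₁) + p₂(1−p₂)] / (p₁−p₂)²

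= (1.960 + 1.282)² × (0.2400 + 0.1875) / 0.0225 = 10.507 × 19 = 199.6, so 200 per arm and 400 in total. The target reproduces. The other scenarios give 120.8, 126.1 and 181.0 against the stated 121, 126 and 181. With the pooled-variance test, power at 200 per arm is 89.6%. None of these calculations uses site or stage.

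**2. Approximate size of the effect.** Let R² be the share of outcome variance explained by site and stage. If minimisation balanced both perfectly, the unadjusted z statistic under the null would have standard deviation √(1−R²) instead of 1, so

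true alpha ≈ 2 × Φ(−1.960 / √(1−R²)).

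- R² = 4.0%: 1.960 / 0.9798 = 2.000, alpha 4.5%
- R² = 13.4%: 1.960 / 0.9306 = 2.106, alpha 3.5%
- R² = 25.7%: 1.960 / 0.8620 = 2.274, alpha 2.3%

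**3. Simulation.** From the protocol: N = 400, 1:1 allocation, minimisation on site and three-level stage, 60% against 75%. Assumed, because the protocol does not give them: 20 equal sites, stage shares 40/30/30%, biased-coin probability 0.8, and the effects in the first column (site SD on the logit scale / log-odds per stage level). The adjusted analysis is a linear risk-difference model with site and stage. There were 4,000 runs per null cell and 2,000 per power cell.

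| Site SD / stage effect | R² | Alpha, chi-square | Alpha, adjusted | Power, chi-square | Power, adjusted |
|---|---|---|---|---|---|
| 0 / 0 | 0% | 5.0% | 5.0% | 89.2% | 88.9% |
| 0.4 / 0.2 | 4.0% | 4.2% | 4.8% | 90.8% | 90.9% |
| 0.8 / 0.4 | 13.4% | 3.5% | 5.2% | 90.3% | 92.8% |
| 1.2 / 0.8 | 25.7% | 2.6% | 4.4% | 91.6% | 95.6% |

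Monte Carlo standard errors are about √(0.05 × 0.95 / 4,000) = 0.34 points for alpha and √(0.9 × 0.1 / 2,000) = 0.67 points for power. The simulated alphas agree with step 2 within that error.

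**4. Is minimisation the cause?** With simple randomisation and R² = 13.4%, the chi-square alpha was 4.6% (2,000 runs), close to nominal. The conservatism comes from ignoring the balanced allocation.

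**5. Sensitivity.** With 15 sites and effects from weak to strong, chi-square alpha fell from about 4.4% to 2.0%, against 4.2 to 5.4% adjusted. Power was 90.4 to 91.7% against 90.9 to 95.5%. Repeat runs at site SD 0.5 and stage log-odds 0.5 gave a chi-square alpha of 4.1 to 4.6%, so modest effects produce only a small departure from 5%.

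**The case against.** **The error is on the safe side.** This stands. A reader might infer that a positive primary result could be spurious. The documents do not support that: every simulated chi-square alpha was at or below nominal within simulation error.

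**Planned power is met.** This also stands. A reader might infer that the trial is underpowered because of the test. Unadjusted power was 89.2 to 91.6% in the table above, against a plan of 90%. The loss is only relative to a better analysis. Section 14 also calls the 362-participant scenario realistic, and 400 exceeds it.

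**Clinic variation may lie mainly in the DOT arm.** VOT records are completed at the study centre (section 18a), so differences in clinic practice may act as a site-by-arm difference more than as a common site effect. With site effects in DOT only, two sets of runs still showed conservatism: 4.0 to 2.7% in one, and 4.2% against 5.1% adjusted in the other. The power gain was about 1 to 2 points. The objection reduces the size but does not remove the point.

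**The adjustment rules could still bring the factors in.** It would be too strong to say that they never could: minimisation with a random element can leave some imbalance, and section 13 is a second route for stage beside section 20b. Both routes still wait for imbalance.

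**The SAP may settle covariates.** It may, but this is not a detail left open. The protocol states an unadjusted test and an imbalance-triggered rule outright, and a SAP that followed it would inherit both.

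**Conclusion.** The point holds as a moderate matter of efficiency and calibration. The stated primary test does not reflect the allocation method, and the stated adjustment rules are unlikely to correct that. If site or stage predicts adherence, the chi-square test is conservative: true alpha is between about 5% (no effect) and about 2% (strong effects), and an adjusted analysis gains about 0 to 4 percentage points of power. If neither factor is prognostic, nothing is lost.

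The facts about the text are certain. The size is not: it rests on assumed numbers of sites (15 or 20), stage shares, biased-coin probability and effect sizes, none of which the protocol gives.

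**What to change.** - Make the primary analysis adjusted for stage (three levels) and site whatever the observed balance. Suitable forms are a regression-standardised risk difference or a Mantel-Haenszel risk difference, with 95% CI. Either keeps the result on the scale used for the sample size.
- Fix the rule for pooling very small sites before the data are seen. Site by stage can be sparse: 20 sites × 3 stages would be 60 cells, or about 400 / 60 = 6.7 participants each. Main effects of site and stage match what minimisation balances.
- For these two factors, replace the imbalance-triggered rules in sections 13 and 20b.
- Keep the chi-square or Fisher test as a supportive unadjusted analysis.
- Apply the same adjustment to secondary outcomes where event numbers allow, and keep an unadjusted or exact test for sparse ones.

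The cost is revised wording, slightly more analysis work and the pooling rule. Both factors are known for every participant at randomisation, so no further data are needed.

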### *Secondary Outcome measures:*

#### *Collected continuously:*

- Proportion of doses observed over 2 months (continuous variable – comparison of means)
- Proportion of doses observed over 6 months (continuous variable – comparison of means)
- Reported side effects

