#### *Collected directly by study at baseline and through telephone interview of participant at 2 and 6 months:*

- Quality of Life (EQ5D)
- Participant satisfaction (Likert scale)
- Participant resource use for DOT/VOT (Participant time, missed work)
- Employment
- Hospitalisation

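### The two secondary adherence proportions are defined as comparisons of means, but the protocol tests every continuous variable with the Wilcoxon rank-sum test, which does not compare means

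*Protocol*

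**What the plan says.** Protocol section 12, under the secondary outcomes collected continuously, lists "Proportion of doses observed over 2 months (continuous variable – comparison of means" and "Proportion of doses observed over 6 months (continuous variable – comparison of means". Section 20a covers both primary and secondary outcomes. It assigns chi-square or Fisher's exact tests to categorical outcomes and then states "Continuous variables will be compared across groups using the Wilcoxon rank-sum test". It makes no exception for the adherence proportions.

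EQ-5D heads a group of measures described in section 12 as "Collected directly by study at baseline and through telephone interview of participant at 2 and 6 months". Section 18a confirms the baseline measurement when it describes the baseline form: "It will also include the validated EQ-5D quality of life scale". Section 20a mentions no baseline term. Section 20b allows covariate adjustment only under conditions: "Where there is evidence of unbalanced randomisation, secondary analysis of unbalanced variables will be adjusted for in analyses, if they are associated with outcome".

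**The concern.** The rank-sum test asks whether values in one arm tend to exceed values in the other. It answers a question about means only under restrictive conditions, such as one distribution being a shifted copy of the other. A bounded proportion of observed doses is unlikely to behave like that, and the protocol's own rules push values towards the ends of the scale. Section 18b counts sessions after loss to follow-up as not completed, section 11b foresees participants who never take up the allocated mode, and section 20a counts doses during a hospital stay as observed.

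At stake is which question the two adherence outcomes answer. If the conflict stays, someone must choose between a mean comparison and a rank comparison later, possibly with the data in view, and the two can give different verdicts. The EQ-5D matter is smaller: a baseline value that is already collected may go unused, at some cost in precision.

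**Working it through.** **1. The texts side by side.** Section 12 fixes the summary (means) for two named outcomes. Section 20a fixes the test (rank-sum) for all continuous variables, and these two outcomes are labelled continuous. Both statements stand in the protocol and they cannot both govern the analysis.

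**2. The plan's own figures.** The only power calculation is Table 1 in section 14, for the binary primary outcome, "with 90% power at the 5% significance level (2 sided) with equal numbers in intervention and control arms". With n per arm = (z₀.₉₇₅ + z₀.₉₀)² × [p₁(1 − p₁) + p₂(1 − p₂)] / (p₁ − p₂)²:

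- 60% vs 75%: (1.960 + 1.282)² × (0.2400 + 0.1875) / 0.0225 = 10.51 × 19.0 = 199.6, so 200 (stated 200).
- The other three scenarios, rounded up, give 121 (50% vs 70%; stated 121), 127 (40% vs 60%; stated 126) and 181 (65% vs 80%; stated 181).

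Table 1 therefore reproduces to within one participant. It is used here only for the planning scenario and for the arm size: "We will aim to recruit 400 participants into the trial over a two year period", that is, 200 per arm.

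**3. Size of the disagreement.** Inputs from section 14: 200 per arm, 5% two-sided, 60% vs 75% of participants above 80% of doses. Assumption, because the protocol gives no distribution: several shapes for the values below 80%, with shapes the same in both arms so that only the share above 80% differs. Each simulated trial was analysed by both tests.

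| Scenario | Wilcoxon rejects | Welch rejects |
|---|---|---|
| 60% vs 75% | about 72–75% | about 76–83% |
| 60% vs 75%, a second set of assumed shapes | about 74–75% | 78–86% |
| 60% vs 60% (no difference) | about 5% | about 5% |

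In the 60% vs 75% scenario, the two tests disagree in about 14% of trials. In these settings the rank test loses some power for the stated comparison, and neither test inflates false positives.

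**4. EQ-5D.** If the baseline and follow-up scores correlate at r, adjusting for baseline multiplies the variance of the treatment difference by 1 − r². The documents give no r, so a range is shown:

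| Assumed r | 1 − r² | Variance cut | Equivalent gain in participants |
|---|---|---|---|
| 0.3 | 0.91 | 9% | 1/0.91 − 1 = 10% |
| 0.5 | 0.75 | 25% | 1/0.75 − 1 = 33% |
| 0.7 | 0.51 | 49% | 1/0.51 − 1 = 96% |

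**The case against.** The best defence is that the bracketed note in section 12 may only mark continuous as against dichotomised handling, since the primary outcome carries a parallel note about binary aggregation. Means could be reported beside a rank-test p-value, and effect estimates with intervals are commonly left to a statistical analysis plan, which may exist but is not shown. It stands that the lack of a stated effect measure or interval is no fault of this protocol. The conflict remains all the same, because the protocol itself names a comparison of means in one place and a test that does not make that comparison in the other.

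A reader might infer that the rank test could routinely declare a difference where the means are equal. Such cases can be built. With 30% of one arm at zero and the rest Beta(18,2), against Beta(6.3,3.7) in the other arm, both means are 0.63, yet Wilcoxon rejects in about 100% of trials and Welch in 4.75%. But that construction puts 64% of one arm and 12% of the other above 80% of doses, a gap of 52 points against the 15 that section 14 plans for. It shows what is possible, not what to expect here.

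A reader might also infer that the cost-effectiveness analysis is compromised. The protocol does not support this: section 20a does not assign the Wilcoxon test to the economic evaluation, QALYs are never mentioned, and an economic analysis is normally specified separately.

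Finally, it would be too strong to say that baseline EQ-5D is ignored. Section 20b could bring it in conditionally, and section 20a does not say whether the rank test applies to follow-up values or to changes. A rank test on EQ-5D is also valid, so the point there concerns efficiency only.

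**Conclusion.** Sections 12 and 20a conflict on the two adherence proportions and should be reconciled. That conclusion rests on the text alone. Its size rests on assumed distributions: under shapes consistent with the planning scenario, the choice of test moves power by a few points up to about 11 (for example 75% against 86%) and changes the verdict in roughly one trial in seven. Larger disagreement needs more extreme shapes.

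Baseline adjustment of EQ-5D is a separate and nearly free improvement. Its size depends entirely on the assumed correlation.

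The binary primary outcome, its chi-square or Fisher's exact test and the target of 400 are unaffected.

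**What to change.** For the proportions of doses observed over 2 and 6 months, state that the analysis is a difference in means with a robust or bootstrap 95% confidence interval, adjusted for the minimisation factors in section 16a (site and stage of treatment), with the Wilcoxon rank-sum test as a sensitivity analysis. Amend the sentence in section 20a so that it no longer overrides section 12.

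For EQ-5D, specify that follow-up values at 2 and 6 months are analysed with the baseline value as a covariate regardless of observed imbalance, in place of the conditional secondary adjustment in section 20b.

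Both are wording changes, to be made before the outcome data are analysed. They need no new data, visits or participants.
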